9.1.9.1 Definitions and Procedures for Contraception and Pregnancy Avoidance

The following definitions apply for contraception and pregnancy avoidance procedures.

* A woman is considered a woman of childbearing potential, ie, fertile, following menarche and until becoming postmenopausal unless permanently sterile. Permanent sterilization methods include hysterectomy, and bilateral oophorectomy. A postmenopausal state is defined as no menses for 12 months without an alternative medical cause. A high FSH level in the postmenopausal range (FSH>40 IU/L) may be used to confirm a postmenopausal state in younger women (eg, those <45 years old) or women who are not using hormonal contraception or hormonal replacement therapy. However, in the absence of 12 months of amenorrhea, a single FSH measurement is insufficient.

The following procedures apply for contraception and pregnancy avoidance.

- 1. Highly effective methods of contraception are defined as "those, alone or in combination, that result in a low failure rate (ie, less than 1% failure rate per year when used consistently and correctly)". In this study, where medications and devices containing hormones are included, the only acceptable methods of contraception are:
 - Nonhormonal methods:
 - IUD.
 - Bilateral tubal occlusion.

- Vasectomized partner (provided that partner is the sole sexual partner of the trial participant and that the vasectomized partner has received medical assessment of the surgical success).
- True sexual abstinence, only if this is in line with the preferred and usual lifestyle of the subject. True abstinence is defined as refraining from heterosexual intercourse during the entire period of the study, from 1 month prior to the first dose, throughout the duration of the study, and for 30 days after completion of the study.
- Hormonal Methods. (Vortioxetine has been shown not to interact with hormonal contraceptives.)
 - Combined (estrogen and progestogen) hormonal contraception associated with inhibition of ovulation initiated at least 3 months prior to the first dose of study drug OR combined with a barrier method (male condom, female condom or diaphragm) if for shorter duration until she has been on contraceptive for 3 months:
 - Oral.
 - Intravaginal (eg, ring).
 - Transdermal.
 - Progestogen-only hormonal contraception associated with inhibition of ovulation initiated at least 3 months prior to the first dose of study drug OR combined with a barrier method (male condom, female condom or diaphragm) if shorter till she has been on contraceptive for 3 months:
 - Oral.
 - Injectable.
 - Implantable.
- 2. Effective methods of contraception (there may be a higher than 1% failure rate) are:
 - Double-barrier method (contraceptive sponge, diaphragm or cervical cap with spermicidal jellies or creams PLUS male condom).
 - Progestogen only hormonal contraception, where inhibition of ovulation is not the primary mode of action PLUS condom with or without spermicide.
- 3. Unacceptable methods of contraception are:
 - Periodic abstinence (eg. calendar, ovulation, symptothermal, postovulation methods).
 - Spermicides only.
 - Withdrawal.
 - No method at all.

- Use of female and male condoms together.
- Cap/diaphragm/sponge without spermicide and without condom.
- 4. Subjects will be provided with information on highly effective/effective methods of contraception as part of the subject informed consent process and will be asked to sign a consent form stating that they understand the requirements for avoidance of pregnancy, donation of ova donation during the course of the study.
- 5. During the course of the study, regular urine hCG pregnancy tests will be performed only for women of childbearing potential. Women of childbearing potential will receive continued guidance with respect to the avoidance of pregnancy and ova donation as part of the study procedures. Such guidance should include a reminder of the following:
 - a) Contraceptive requirements of the study.
 - b) Reasons for use of barrier methods (ie, condom).
 - c) Assessment of subject compliance through questions such as:
 - i. Have you used the contraception consistently and correctly since the last visit?
 - ii. Have you forgotten to use contraception since the last visit?
 - iii. Are your menses late? (even in women with irregular or infrequent menstrual cycles a pregnancy test must be performed if the answer is "yes").
 - iv. Is there a chance you could be pregnant?
- 6. In addition to a negative urine hCG pregnancy test at Screening, Female subjects of childbearing potential must also have confirmed menses in the month before first dosing (no delayed menses), a negative urine hCG pregnancy test prior to receiving any dose of study medication (as close as possible and prior to first dose of study medication, preferably on the same day).

9.1.10 Pregnancy

If any subject is found to be pregnant during the study she should be withdrawn and any sponsor-supplied drug should be immediately discontinued.

If the pregnancy occurs during administration of active study medication, eg, after Visit 2 or within 30 days of the last dose of active study medication, the pregnancy should be reported immediately, using a pregnancy notification form, to the contact listed in Section 1.1.

Should the pregnancy occur during or after administration of blinded drug, the investigator must inform the subject of their right to receive treatment information. If the subject chooses to receive unblinded treatment information, the individual blind should be broken by the investigator.

If the female subject agrees to the primary care physician being informed, the investigator should notify the primary care physician that the subject was participating in a clinical study at the time she became pregnant and provide details of treatment the subject received.

All reported pregnancies will be followed up to final outcome, using the pregnancy form. The outcome, including any premature termination, must be reported to the sponsor. An evaluation after the birth of the child will also be conducted.

9.1.11 PGx Sample Collection

When sampling of whole blood for PGx analysis occurs, every subject must sign informed consent/be consented in order to participate in the PGx sample analysis.

Two 3-mL whole blood samples for DNA isolation will be collected at the Baseline Visit before dosing from each subject in the study, into plastic K₂EDTA spray-coated tubes, and stored under frozen conditions.

Two whole blood samples (2.5 mL per sample) for RNA isolation will be collected at the Baseline Visit before dosing and at the Week 12/Early Termination (Visit 6) into PAXgene tubes, and stored under frozen conditions.

DNA forms the basis for the genes that make the body produce proteins such as enzymes, drug transporters or drug targets, and may be evaluated for the genetic contribution how the drug is broken down, or how the drug affects the body. This is called a "Pharmacogenomics research study." Specific purposes of this study include:

- Identifying genetic reasons why certain people respond differently to vortioxetine.
- Finding out more information about how vortioxetine works.
- Generating information needed for research, development, and regulatory approval of tests to predict response to vortioxetine.
- Identifying variations in genes related to the biological target of vortioxetine.

This information may be used, for example, to develop a better understanding of the safety and efficacy of vortioxetine and other study medications, and for improving the efficiency, design and study methods of future research studies.

If necessary and feasible, a second aliquot of blood may be taken if isolation of DNA from the first sample was not successful or possible.

The samples will be stored for no longer than 15 years after completion of the study or vortioxetine is no longer actively pursued by Takeda or its collaborators. No samples will be stored for longer than permitted by the applicable law and samples will be destroyed upon notification from Takeda.

Detailed instructions for the handling and shipping of samples are provided in the Laboratory Manual.

9.1.12 Documentation of Screen Failure

Investigators must account for all subjects who sign informed consent.

If the subject is withdrawn at screening, the investigator should complete the eCRF. The IxRT should be contacted as a notification of screen failure.

The primary reason for screen failure is recorded in the eCRF using the following categories:

- PTE/AE.
- Did not meet inclusion criteria or did meet exclusion criteria (specify reason)
- Significant protocol deviation.
- Lost to follow-up.
- Voluntary withdrawal (specify reason).
- Study termination.
- Other (specify reason).

Subject identification numbers assigned to subjects who fail screening should not be reused.

9.1.13 Documentation of Study Entrance

Only subjects who meet all of the inclusion criteria and none of the exclusion criteria are eligible for entrance into the treatment phase.

If the subject is found to be not eligible for treatment phase, the investigator should record the primary reason for failure on the applicable eCRF.

9.2 Monitoring Subject Treatment Compliance

Subjects will be required to bring study medication containers/unused study medication to each dispensing site visit. All supplies used to administer study drug to the subject will be recorded on the eCRFs.

If a subject is persistently noncompliant with study drug (eg, less than 70% compliant or greater than 125% compliant between visits), it may be appropriate to withdraw the subject from the study. All subjects should be reinstructed about the dosing requirement during study contacts. The authorized study personnel conducting the re-education must document the discussion in the subject source records.

9.3 Schedule of Observations and Procedures

The schedule for all study-related procedures for all evaluations is shown in Appendix A. Assessments should be completed at the designated visit/time point(s).

9.3.1 Screening Visit 1 (Days -21 to -1)

Subjects will may be screened within 21 days prior to Baseline. Procedures to be completed during the Screening Visit are detailed in Appendix A. Subjects will be screened in accordance with predefined inclusion and exclusion criteria as described in Section 7.0. See Section 9.1.12 for

procedures for documenting screening failures. IxRT will be accessed for the subject screening number. The factors for determining a change/discontinuation from the prior antidepressant as assessed by the subject and by the investigator will be collected. The Screening and Baseline Visits may be combined if determined appropriate per the investigator. Any procedure that is to be performed at both visits should only be conducted once for a combined visit.

9.3.2 Study Entrance/Baseline Visit 2 (Day 1)

Study enrollment will take place on Day 1 (Baseline, Visit 2). Procedures to be completed during the Baseline Visit are detailed in Appendix A.

If the subject has satisfied all of the inclusion criteria and none of the exclusion criteria for enrollment, the subject should be enrolled and study drug should be dispensed using the IxRT, as described in Section 8.2. Subjects will be instructed on when to take the first dose of study drug. The procedure for documenting Screening failures is provided in Section 9.1.12. The factors for determining a change/discontinuation from the prior antidepressant as assessed by the subject and by the investigator will be collected.

9.3.3 Open-Label Treatment Visits 3 and 5: Week 2 (Day 15), and Week 6 (Day 43)

The Subjects will return to the study site for their Week 2 (Visit 3) and Week 6 (Visit 5) Visits. Subjects will be instructed to return their bottle of study drug dispensed at the previous visit for drug accountability. Procedures to be completed during Visits 3 and 5 are detailed in Appendix A.

9.3.4 Telephone Visit 4 and 6: Week 4 (Day 29) and Week 9 (Day 64)

A telephone visit will occur at Visit 4 (Week 4) and 6 (Week 9). Procedures to be completed during Visits 4 and 6 are detailed in Appendix A.

9.3.5 Final Visit or Early Termination

The Final Visit will be performed at Visit 7 (Week 12) or at Early Termination Visit. For all subjects receiving study drug, the investigator must complete the End of Study eCRF page. Procedures to be completed during Final Visit/Early Termination Visit are detailed in Appendix A.

For subjects who permanently discontinue study drug early, all Final Visit/Early Termination assessments detailed in Appendix A should be performed in close proximity to, or at the time of, study drug discontinuation.

At the End of Study Visit the Clinician and subject satisfaction with the antidepressant treatment will be collected. In addition, Clinician and subject satisfaction with the GAS approach as a method for establishing treatment goals, evaluating progress towards treatment goals, and improving communication between clinicians and patients will be collected.

9.3.6 Unscheduled Visit

Unscheduled visits may occur at any time after the Week 2 visit.

Subjects may return to the study center for unscheduled visits as needed. Unscheduled study visits can be performed when the subject has a study related issue in between regular study visits. The following procedures should be performed during this visit:

- Concomitant medications.
- AE assessment.
- Other procedures, including dose adjustments, as deemed appropriate by the investigator.

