6.2.2 Dose

In the current study, dosing (both initial and adjustments) will be determined by the treating physician as per routine clinical practice. The recommended starting dose is 10 mg administered orally once daily without regard to meals as per the Trintellix US Package Insert. Dosage should then be increased to 20 mg/day, as tolerated, because higher doses demonstrated better treatment effects in studies conducted in the United States. The effectiveness and safety of doses above 20 mg/day have not been evaluated in controlled clinical studies. A dose decrease down to 5 mg/day may be considered for subjects who do not tolerate higher doses. The dose can be reduced/increased/interrupted due to a particular AE.

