8.1.1.1 Study drug

Vortioxetine is a compound developed by Takeda and H. Lundbeck A/S as an antidepressant and treatment for MDD. Vortioxetine was approved in September 2013 and commercialized in the United States in January 2014. Vortioxetine belongs to a new chemical class of psychotropics, the bis-arylsulfonyl amines, which possess unique properties compared with currently known psychotropics. This class of compounds is structurally different from all currently known psychotropics.

Vortioxetine is commercially formulated as immediate-release tablets intended for oral administration

The study drug will be packaged in high-density polyethylene bottle with child resistant closures. Each bottle contains 28 daily doses plus 7 extra tablets for a total of 35 tablets per bottle to be dispensed at the visits indicated in the Schedule of the Study Procedures (Appendix A). The subjects will be required to take 1 tablet orally, at the same time of day, preferably in the morning, or as directed. The study drug will be labeled with a single label and dispensed as open-label for the 12-week treatment phase. The study drug will be identifiable by a unique identification (ID) number that will be assigned by an IxRT. Each bottle will be labeled with pertinent study information.

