8.2 Study Drug Assignment and Dispensing Procedures

Subjects will be assigned to begin the study drug with the recommended starting dose of 10 mg/day administered orally once daily without regard to meals. Based on the discretion of the investigator or designee, dosage should then be increased to 20 mg/day, as tolerated, because higher doses demonstrated better treatment effects in trials conducted in the United States. A dose decrease down to 5 mg/day may be considered for subjects who do not tolerate higher doses. The investigator (or designee) may increase or decrease the dosage at any time. Dose adjustments should occur during regularly scheduled visits, or subjects should return for an unscheduled visit.

The investigator or the investigator's designee will access the IxRT at Screening to obtain the subject study number. The investigator or the investigator's designee will utilize the IxRT to enroll the subject into the study. During this contact, the investigator or designee will provide the necessary subject-identifying information, including the subject number assigned at Screening.

The medication ID number of the sponsor-supplied drug to be dispensed will then be provided by the IxRT. If sponsor-supplied drug (vortioxetine) is lost or damaged, the site can request a replacement from IxRT (refer to IxRT manual provided separately). At subsequent drug-dispensing visits, the investigator or designee will again access IxRT to request additional sponsor-supplied drug for a subject. The medication ID number of the study drug to be dispensed will be provided by the IxRT.

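### Protocol 9.3.6 dates unscheduled visits from the Week 2 visit, which conflicts with its own later sentences and with 8.2 and, read literally, leaves no visit for an early step-down to 5 mg

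*Protocol*

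**What the plan says.** Four parts of the protocol bear on when a dose can be lowered.

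- **Unscheduled visits (Protocol 9.3.6).** The section opens with a start time: "Unscheduled visits may occur at any time after the Week 2 visit". It continues: "Subjects may return to the study center for unscheduled visits as needed". A third sentence ties these visits to study-related issues arising between regular visits. The procedures listed for such a visit include: "Other procedures, including dose adjustments, as deemed appropriate by the investigator".
- **Dose changes (Protocol 8.2 and 6.2.2).** Section 8.2 starts subjects on 10 mg/day and adds: "A dose decrease down to 5 mg/day may be considered for subjects who do not tolerate higher doses". On timing it says: "The investigator (or designee) may increase or decrease the dosage at any time". On setting it says: "Dose adjustments should occur during regularly scheduled visits, or subjects should return for an unscheduled visit". Footnote (h) of Appendix A repeats that last instruction. Section 6.2.2 adds: "The dose can be reduced/increased/interrupted due to a particular AE". Footnote (a) to the study schematic in Protocol 6.1, repeated in SAP 4.4, lets the investigator lower the dose to 5 mg/day and names no earliest date.
- **Schedule (Protocol 6.1 and Appendix A).** After Baseline on Day 1, the next contact of any kind is the Week 2 visit, Day 15 ±3. Appendix A marks dose adjustment at Weeks 2 and 6.
- **Supply (Protocol 8.1.1.1 and Appendix A).** Tablets come in 5, 10 and 20 mg. "The subjects will be required to take 1 tablet orally, at the same time of day, preferably in the morning, or as directed". Bottles are dispensed at the visits shown in Appendix A, which are Baseline, Week 2 and Week 6.

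The opening sentence of 9.3.6 is current text. Appendix E lists no change to it under Amendment 1.

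**The concern.** The protocol gives the investigator freedom to lower the dose at any point and names two kinds of visit at which to do it. In roughly the first two weeks neither kind is available if the opening sentence of 9.3.6 is applied as written: no visit is scheduled, and unscheduled visits have not yet begun. These are the first weeks on 10 mg, when a subject who cannot tolerate that dose may need the lower one.

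What is at stake is the care of that subject. The permission to reduce exists, but the literal text provides no visit at which to act on it. Because the section also contains broader sentences, the approximately 25 sites could resolve the conflict differently.

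**Working it through.** No sample size, rate or error probability enters, and the plan states no figure to reproduce. The check sets the texts side by side. The only arithmetic is the visit window.

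**1. Length of the interval.** Appendix A puts the Week 2 visit at Day 15 ±3.

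- Earliest: 15 − 3 = Day 12. Latest: 15 + 3 = Day 18.
- The interval without a scheduled contact therefore runs from Day 2 to the day before that visit: Day 11 at the earliest, Day 14 on schedule, Day 17 at the latest.

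**2. Visits available for a dose change in that interval.**

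| Type of visit named in 8.2 | Available from Day 2 until the Week 2 visit? |
|---|---|
| Regularly scheduled | No. Neither a site visit nor a telephone contact is scheduled. |
| Unscheduled, by the opening sentence of 9.3.6 | No. Such visits are dated from after the Week 2 visit. |
| Unscheduled, by the next two sentences of 9.3.6 | Yes, if read alone. They set no start time, and the interval lies between two regular visits. |

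The section gives two answers to the same question. If the later sentences already cover the period from Day 2, the time limit in the opening sentence does nothing. If the limit governs, it blocks what 8.2 and the schematic footnote allow.

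**3. What remains open under the literal reading.** The dose can be interrupted for an adverse event (6.2.2). Subjects may report adverse events at any time (10.2.1.2). An Early Termination Visit exists (9.3.5). The Week 2 visit may fall as early as Day 12. None of these is a visit before Week 2 at which a subject can move to 5 mg and stay on treatment.

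**4. Whether correcting the date is enough.** A subject holding 10 mg tablets and taking one a day needs 5 mg tablets to step down. Section 8.1.1.1 ties dispensing to the Appendix A visits, and Appendix A has no column for unscheduled visits. Read as literally as 9.3.6, the supply text does not provide for new tablets at any unscheduled visit, early or late. Moving the start date alone would open the visit without settling whether 5 mg tablets can be handed out there.

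**The case against.** The strongest reply is that a sensible site would never be stopped. The opening sentence is permissive and does not contain the word only. The two sentences after it cover the early interval, the procedure list includes dose adjustment, and 8.2 uses should rather than must. The schematic footnote and footnote (h) carry no Week 2 limit. On this view the subject has a visit and the text is merely untidy.

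Much of that stands. A reader might infer that the protocol forbids an early reduction or leaves the subject without recourse. The documents do not support that: other text permits the reduction, and interruption, adverse event reporting and early termination are all available. What does not fall away is the conflict itself. One sentence sets an explicit start time, the others set none, and the protocol does not say which governs or why Week 2 was chosen.

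A reader might also infer that the wording pushes subjects toward interruption or withdrawal and so erodes the number of completers. No text in either document shows this, and neither gives a rate of early intolerance from which to estimate it.

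**Conclusion.** The conflict is real and small. The opening sentence of 9.3.6 disagrees with the rest of its own section, with 8.2 and with the schematic footnote. On the literal reading, from Day 2 until the Week 2 visit on Day 15 ±3, a subject who does not tolerate 10 mg has no visit for stepping down to 5 mg. That conclusion assumes the explicit time limit prevails over the general sentences. If a site reads it the other way, the visit is available and only the inconsistency remains.

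Subjects who tolerate 10 mg are unaffected, and the number who do not cannot be obtained from the documents. This is a tolerability and patient-safety matter. It changes no planned analysis: the full analysis set counts subjects as vortioxetine-treated whatever dose they received (SAP 7.2). The change is worth making at the next amendment but is not critical.

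**What to change.** Two edits to the protocol:

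1. In the opening sentence of 9.3.6, replace the reference to the Week 2 visit with the Baseline Visit, so that unscheduled visits may take place at any time after Baseline.
2. In 9.3.6, or in footnote (h) of Appendix A, state that study drug may be dispensed through the IxRT at an unscheduled visit when the dose is adjusted.

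The cost is two short text changes, a check that the IxRT can release 5 mg tablets at such a visit, and possibly a few additional unscheduled visits. Sample size, scheduled visits and the SAP stay as they are.
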